9.1.3.2. Impact of Weight on Quality of Life Lite Clinical Trials Version

The IWQOL-Lite-CT is a 20-item, obesity-specific PRO instrument developed for use in obesity clinical trials. It assesses two primary domains of obesity-related HRQoL: physical (7 items), and psychosocial (13 items). A 5-item subset of the physical domain – the physical function composite is also supported. Items in the physical function composite describe physical impacts related to general and specific physical activities. All items are rated on either a 5-point frequency ("never" to "always") scale or a 5-point truth ("not at all true" to "completely true") scale. (Kolotkin et al. 2017, 2018).

9.1.3.3. EQ-5D-5L

Generic health-related quality of life will be assessed using the EQ-5D-5L (EuroQoL Group 2015). The EQ-5D-5L is a standardized 5-item instrument for use as a measure of health outcome. It provides a simple descriptive profile and a single index value for health status that can be used in the clinical and economic evaluation of health care as well as population health surveys. The EQ-5D-5L comprises 5 dimensions of health (mobility, self care, usual activities, pain/discomfort, and anxiety/depression). The 5L version, introduced in 2005, scores each dimension at 5 levels (no problems, slight problems, moderate problems, severe problems, unable to perform/extreme problems), for a total of 3125 possible health states. In addition to the health profile, a single health state index value can be derived based on a formula that attaches weights to each of the levels in each dimension. This index value ranges between less than 0 (where 0 is a health state equivalent to death; negative values are valued as worse than dead) to 1 (perfect health). In addition, the EQ Visual Analog Scale records the respondent's self-rated health status on a vertical graduated (0 to 100) visual analog scale. In conjunction with the health state data, it provides a composite picture of the respondent's health status.

The EQ-5D-5L is used worldwide and is available in more than 170 different languages. Details on the instrument, and scoring, organizing, and presenting the data collected can be found in the EQ-5D-5L User Guide (EuroQoL Group 2015).

9.1.3.4. Patient Global Impression of Status for Physical Activity

Study participants will be asked to complete a Patient Global Impression of status (PGIS) item specifically developed for this study. This is a patient-rated assessment of current health limitation and is rated on a 5-point scale ranging from "1 not at all limited" to "5 extremely limited."

9.1.4. Appropriateness of Assessments

Efficacy and safety assessments included in this study are generally regarded as reliable and accurate with respect to the efficacy and safety assessments in individuals and populations with Obesity.

9.2. Adverse Events

All AEs will be collected from the signing of the ICF until the time points specified in the Schedule of Activities (Section 2).

Care will be taken not to introduce bias when detecting AEs and/or SAEs. Open ended and non leading verbal questioning of the participant is the preferred method to inquire about AE occurrences.

Investigators are responsible for monitoring the safety of participants who have entered this study and for alerting Lilly or its designee to any event that seems unusual, even if this event may be considered an unanticipated benefit to the participant.

The investigator is responsible for the appropriate medical care of participants during the study.

Investigators must document their review of each laboratory safety report.

The investigator remains responsible for following, through an appropriate health care option, AEs that are serious or otherwise medically important, considered related to the investigational product or the study, or that caused the participant to discontinue the investigational product before completing the study. The participant should be followed until the event resolves, stabilizes with appropriate diagnostic evaluation, or is reasonably explained. The frequency of follow-up evaluations of the AE is left to the discretion of the investigator.

Lack of drug effect is not an AE in clinical studies, because the purpose of the clinical study is to establish treatment effect.

The investigator will record all relevant AE and SAE information in the eCRF. After the ICF is signed, study site personnel will record via eCRF the occurrence and nature of each participant's preexisting conditions, including clinically significant signs and symptoms of the disease under treatment in the study. In addition, site personnel will record any change in the condition(s) and any new conditions as AEs. Investigators should record their assessment of the potential relatedness of each AE to protocol procedure, investigational product, via eCRF.

The investigator will interpret and document whether or not an AE has a reasonable possibility of being related to study treatment, study device, or a study procedure, taking into account the disease, concomitant treatment or pathologies.

A "reasonable possibility" means that there is a cause and effect relationship between the investigational product, study device and/or study procedure and the AE.

The investigator answers yes/no when making this assessment.

Planned surgeries and nonsurgical interventions should not be reported as AEs unless the underlying medical condition has worsened during the course of the study.

If a participant's investigational product is discontinued as a result of an AE, study site personnel must report this to Lilly or its designee via eCRF, clarifying if possible, the circumstances leading to any dosage modifications, or discontinuations of treatment.

Please refer to Appendix 6 Adverse Events: Definitions and Procedures for Recording, Evaluating, Follow-up, and Reporting.

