Investigators are not obligated to actively seek AEs or SAEs in participants once they have discontinued and/or completed the study (the participant disposition CRF has been completed). However, if the investigator learns of any SAE, including a death, at any time after a subject has been discharged from the study, and he or she considers the event reasonably possibly related to the study treatment or study participation, the investigator must promptly notify Lilly.

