9.2.1.1. Suspected Unexpected Serious Adverse Reactions

Suspected unexpected serious adverse reactions (SUSARs) are serious events that are not listed in the IB and that the investigator identifies as related to investigational product or procedure. United States 21 CFR 312.32 and European Union Clinical Trial Directive 2001/20/EC and the associated detailed guidances or national regulatory requirements in participating countries require the reporting of SUSARs. Lilly has procedures that will be followed for the identification, recording, and expedited reporting of SUSARs that are consistent with global regulations and the associated detailed guidances.

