# 6.13.1. Analysis of Adverse Events

## 6.13.1.1. Treatment Emergent Adverse Events

A treatment-emergent adverse event (TEAE) is defined as an event that first occurred or worsened in severity after baseline. The MedDRA Lowest Level Term (LLT) will be used in the treatmentemergent derivation. The maximum severity for each LLT during the baseline period including ongoing medical history will be used as baseline severity. For events with a missing severity during the baseline period, it will be treated as "mild" in severity for determining treatment-emergence. Events with a missing severity during the postbaseline period will be treated as "severe" and treatment-emergence will be determined by comparing to baseline severity.

For events occurring on the day of first taking study medication, the case report form (CRF)collected information (for example, treatment emergent flag, start time of study treatment and event) will be used to determine whether the event was pre- versus post-treatment if available. If the relevant information is not available, then the events will be counted as post-treatment.

The counts and percentages of participants with TEAEs will be summarized by treatment using MedDRA Preferred Term (PT) nested within System Organ Class (SOC). Statistical comparisons will be applied at both the SOC and PT levels. Events will be ordered by decreasing frequency within SOC. The SOC will be in alphabetical order. For events that are sex-specific, the denominator and computation of the percentage will include only participants from the given sex.

An overview of the number and percentage of participants who experienced a TEAE, serious adverse event (SAE), death, discontinued from study treatment or study due to an AE, relationship to study drug will be summarized by treatment.

The counts and percentages of patients with TEAEs by maximum severity will be summarized by treatment using MedDRA PT. For each participant and TEAE, the maximum severity for the MedDRA PT is the maximum postbaseline severity observed from all associated LLTs mapping to the MedDRA PT. The maximum severity will be determined based on the nonmissing severities. If all severities are missing for the defined postbaseline period of interest, it will show as missing in the table.

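### Protocol Section 9.2 defines a reasonable possibility of relatedness as an existing causal relationship, which contradicts the possibility standard around it and leaves the yes/no answer open to two readings

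*Protocol*

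**What the plan says.** Section 9.2 of the protocol words the causality judgement in four steps.

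- It opens with potential: "Investigators should record their assessment of the potential relatedness of each AE".
- It then puts the question to be documented, which is "whether or not an AE has a reasonable possibility of being related to study treatment, study device, or a study procedure". The investigator is to weigh the disease and other treatments or conditions in answering.
- It defines the key phrase. A reasonable possibility, it says, "means that there is a cause and effect relationship between the investigational product, study device and/or study procedure and the AE".
- It fixes the scale: "The investigator answers yes/no when making this assessment".

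Other places then use the answer, or a judgement in similar words.

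- Section 9.2.1.1 describes SUSARs as "serious events that are not listed in the IB and that the investigator identifies as related to investigational product or procedure". It adds: "Lilly has procedures that will be followed for the identification, recording, and expedited reporting of SUSARs".
- Section 9.2.1 requires prompt notice of an SAE learned of after discharge from the study only if "he or she considers the event reasonably possibly related to the study treatment or study participation". For an SAE after consent but before first dose, the sponsor reporting route applies only where a relation to a study procedure is judged reasonably possible.
- Appendix 7 has a comparable condition for pregnancy-related SAEs after the study.
- SAP Section 6.13.1.1 plans an AE overview in which "relationship to study drug will be summarized by treatment".

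**The concern.** The question asks about a possibility, and the definition asks for a fact. An event that the investigator suspects but cannot establish as caused by the product, device or procedure passes the first test and fails the second. With only yes and no available, nothing on the form shows which test was used.

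Two things are at stake. An investigator who applies the definition literally may answer no for suspected reactions, and some reporting routes depend on that answer or on the same kind of judgement. And if some sites follow the definition while others follow the surrounding wording, the related-AE counts mix two standards.

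**Working it through.** No arithmetic applies. The point uses no alpha, power, rate or sample size, and neither document gives a figure for related AEs. The check is a comparison of wording, followed by a trace of what depends on the answer.

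**Step 1. Is the definition stricter than the other relatedness wording?**

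- Section 9.2, recording instruction: potential relatedness.
- Section 9.2, question: a reasonable possibility.
- Section 7.7 (nonstudy medication in participants screened but not randomized): an event that a study procedure may have caused.
- Section 9.2.1, pre-dose and post-discharge SAEs: reasonably possibly related.
- Section 9.2.1.1: the reactions are, by name, suspected ones.
- Section 9.2, definition: a causal relationship exists, with no qualifier such as may or suspected.

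The definition stands alone. Every other place accepts less than established causation.

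**Step 2. Is it corrected elsewhere?** Section 9.2 sends the reader to Appendix 6 for AE definitions. In the pages available, that appendix covers special safety topics and does not define relatedness. Appendix 1 defines AE and TEAE but neither relatedness nor reasonable possibility. The sentence in Section 9.2 is the only definition.

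**Step 3. What happens to a suspected but unproven reaction answered no?**

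- SUSAR status (Section 9.2.1.1): a serious unlisted event falls outside the stated description, because that rests on the investigator's identification. The sponsor has its own procedures, but no sponsor override of the causality answer is described.
- SAE learned of after discharge (Section 9.2.1; Appendix 7 if pregnancy-related): the relatedness condition for notification is not met.
- Procedure-related SAE before first dose (Section 9.2.1): the sponsor SAE route is not triggered. The event is still recorded in the eCRF and assessed for seriousness.
- AE overview (SAP Section 6.13.1.1): the event is missing from the relationship item.
- In-study SAE after first dose (Section 9.2.1): unaffected. Any SAE goes to the sponsor within 24 hours of awareness, with no causality condition.
- TEAE, SAE, death and AE-discontinuation counts (SAP Sections 6.13.1.1, 6.13.1.4 and 6.13.1.5): unaffected, because none filters on relatedness.
- SAE listing (SAP Section 6.13.1.4): all SAEs are included. Only the relationship column changes.

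**Step 4. Direction.** Every event that meets the literal definition also meets the possibility standard, but not the reverse. Where the literal reading is used, the number marked related can therefore only stay the same or fall, in any arm. Where it is not used, nothing changes. Neither document says how many sites would read it which way.

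**The case against.** The strongest reply is that the sentence names the kind of relationship in question, causal and not merely temporal, while the word possibility still sets the threshold. Read with the rest of Section 9.2 and with Section 9.2.1, that is a fair interpretation. A reader might infer that every suspected reaction will be marked unrelated, or that a blinded investigator could almost never answer yes. The documents support neither. What remains is that the sentence does not say what this interpretation needs it to say, and a binary safety item should not depend on which reading a site prefers.

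A reader might also infer that serious suspected reactions would be lost to the sponsor or drop out of expedited reporting. That goes too far. In-study SAEs after first dose reach the sponsor within 24 hours whatever the answer, investigators must also alert the sponsor to unusual events, and the sponsor has its own procedures for identifying SUSARs. What is exposed is classification under the investigator-based description in Section 9.2.1.1.

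Nor would pre-dose SAEs go uncaptured. AEs after consent are recorded in the eCRF, and Section 6.4 lists SAEs among the minimum data for screen failures. Only the reporting route is at risk. The post-discharge gate does depend on relatedness, although it concerns events that investigators are not obliged to seek.

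Finally, the effect on the analysis is small. One overview item and one listing column use relatedness, no endpoint does, and the same definition applies to all arms under blinding. All of this stands and limits the point, but it does not remove the contradiction.

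**Conclusion.** The definition in Section 9.2 contradicts the standard it is meant to define, and nothing else in the protocol corrects it. Read literally, it could under-classify SUSARs, stop notification of SAEs learned of after discharge, close the sponsor route for procedure-related pre-dose SAEs, and lower the relationship item in the SAP overview. It could also make that item inconsistent between sites.

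The size cannot be estimated from the documents. The downward direction is conditional on literal reading, so it would be wrong to call it certain for the trial as a whole. The conclusion also assumes that the investigator's answer stands, since no sponsor override is described. The main safety counts and the 24-hour notification of in-study SAEs after first dose are sound on this point. It is a wording defect in a safety classification rule and is worth correcting.

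**What to change.** Replace the defining sentence in Section 9.2 with one to this effect: a reasonable possibility means that there are facts or reasons to suggest that the investigational product, study device or study procedure may have caused the AE; causation need not be established. This wording is a suggestion and is not taken from the documents.

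Then use the same term in the places that rely on the judgement: the pre-dose and post-discharge conditions in Section 9.2.1, the SUSAR description in Section 9.2.1.1, and the pregnancy-related condition in Appendix 7. Changing Section 9.2 alone would leave three differently worded standards in those places.

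The cost is one reworded sentence, a few aligned phrases and a short update to site training. No endpoint, sample size, dose or visit changes. The downside is that somewhat more AEs will be marked related.

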9.2.1. Serious Adverse Events

An SAE is any AE from this study that results in one of the following outcomes:

- death
- initial or prolonged inpatient hospitalization
- a life-threatening experience (that is, immediate risk of dying)
- persistent or significant disability/incapacity
- congenital anomaly/birth defect
- important medical events that may not be immediately life-threatening or result in death or hospitalization but may jeopardize the participant or may require intervention to prevent one of the other outcomes listed in the definition above. Examples of such medical events include allergic bronchospasm requiring intensive treatment in an emergency room or at home, blood dyscrasias or convulsions that do not result in inpatient hospitalization, or the development of drug dependency or drug abuse.
- when a condition related to the drug delivery system necessitates medical or surgical intervention to preclude either permanent impairment of a body function or permanent damage to a body structure, the serious outcome of "required intervention" will be assigned.

All AEs occurring after signing the ICF are recorded in the eCRF and assessed for serious criteria. The SAE reporting to the sponsor begins after the participant has signed the ICF and has received investigational product. However, if an SAE occurs after signing the ICF, but prior to receiving investigational product, the SAE should be reported to the sponsor per SAE-reporting requirements and timelines (see Section 9.2) if it is considered reasonably possibly related to study procedure.

Study site personnel must alert Lilly or its designee of any SAE within 24 hours of investigator awareness of the event via a sponsor-approved method. If alerts are issued via telephone, they

are to be immediately followed with official notification on study-specific SAE forms. This 24-hour notification requirement refers to the initial SAE information and all follow-up SAE information. Participants with a serious hepatic AE should have additional data collected using the eCRF.

Pregnancy (during maternal or paternal exposure to investigational product) does not meet the definition of an AE. However, to fulfill regulatory requirements any pregnancy should be reported following the SAE process to collect data on the outcome for both mother and fetus. Abnormal pregnancy outcomes (for example, spontaneous abortion, fetal death, stillbirth, congenital anomalies, and ectopic pregnancy) are considered SAEs.

Investigators are not obligated to actively seek AEs or SAEs in participants once they have discontinued and/or completed the study (the participant disposition CRF has been completed). However, if the investigator learns of any SAE, including a death, at any time after a subject has been discharged from the study, and he or she considers the event reasonably possibly related to the study treatment or study participation, the investigator must promptly notify Lilly.

9.2.1.1. Suspected Unexpected Serious Adverse Reactions

Suspected unexpected serious adverse reactions (SUSARs) are serious events that are not listed in the IB and that the investigator identifies as related to investigational product or procedure. United States 21 CFR 312.32 and European Union Clinical Trial Directive 2001/20/EC and the associated detailed guidances or national regulatory requirements in participating countries require the reporting of SUSARs. Lilly has procedures that will be followed for the identification, recording, and expedited reporting of SUSARs that are consistent with global regulations and the associated detailed guidances.

9.2.2. Adverse Event Monitoring with a Systematic Questionnaire

Patients with overweight and obesity are at increased risk for depression (Luppino et al. 2010). Depression can increase the risk for suicidal ideation and behavior. Therefore, study participants will be screened at trial entry and monitored during the study for depression, suicidal ideation and behavior.

Baseline and treatment-emergent assessment of depression, suicidal ideation and behavior will be monitored during the study using the C-SSRS and PHQ-9 (Section 9.4.6).

The C-SSRS is a scale that captures the occurrence, severity, and frequency of suicidal ideation and/or behavior during the assessment period. The scale includes suggested questions to solicit the type of information needed to determine if suicidal ideation and/or behavior occurred. The tool was developed by the National Institute of Mental Health trial group for the purpose of being a counterpart to the Columbia Classification Algorithm of Suicide Assessment categorization of suicidal events.

The PHQ-9 is a validated self-report screening tool that assesses the presence and intensity of depressive symptoms. The PHQ-9, which incorporates the 9 Diagnostic and Statistical Manual-IV depression criteria "0" (not at all) to "3" (nearly every day), was developed for use in primary care settings (Kroenke et al. 2001).

Nonserious AEs obtained through the questionnaire are recorded and analyzed separately. Only *serious* AEs elicited through the C-SSRS or PHQ-9 are to be recorded as AEs via the eCRF and reported to Lilly or its designee within 24 hours as SAEs. For this study, the C-SSRS is adapted for the assessment of the ideation and behavior categories only. The Intensity of Ideation and Lethality of Behavior sections are removed.

9.2.3. Complaint Handling

A product complaint is any written, electronic, or oral communication that alleges a deficiency related to the identity, quality, durability, reliability, safety, effectiveness, or performance of a Lilly product after it is released for distribution. When the ability to use the product safely is impacted, the following are also product complaints:

- Deficiencies in labeling information, and
- Use errors for device or combination products due to ergonomic design elements of the product.

Sponsor collects product complaints on investigational products, medical devices, and drug delivery systems used in clinical studies in order to ensure the safety of study participants, monitor quality, and to facilitate process and product improvements. Complaints are also collected on comparators and other clinical trial material supplied, as required.

Participants will be instructed to contact the investigator as soon as possible if he or she has a complaint or problem with the investigational drug, medical device, or drug delivery system so that the situation can be assessed.

As required by local regulations, and per instructions on the complaint form, the investigator will report to the sponsor and to their IRB/IEC any unanticipated adverse device effect or UADE (unanticipated problem that resulted in an SAE), or any device related product complaint that could have led to an SAE had precautions not been taken.

- For complaints associated with an SAE, report within 24 hours of site/trial personnel becoming aware of the product complaint.
- For any complaint that might have led to an SAE if appropriate action had not been taken, the intervention had not occurred, or circumstances had been less fortunate, report within 24 hours of site personnel becoming aware of the product complaint.
- For complaints not associated with an SAE, report within one business day of site/trial personnel becoming aware of the product complaint, or per the protocol.

